### 3.1.2.1 Definition of Dose-Limiting Toxicity

In this study, a DLT is defined as at least one of the following events occurring during the first cycle (*or the first two cycles in the bridging cohorts for patients with FL who start idasanutlin at Cycle 2*) of treatment and assessed by the investigator as not clearly related to the patient's underlying disease:

- *Any Grade 5 adverse event unless unequivocally due to the underlying malignancy or extraneous causes*
- Adverse event of any grade that leads to a delay of more than 14 days in the start of the next treatment cycle
- Grade 3 or 4 non-hematologic adverse event, with the following exceptions:
  - Grade 3 or 4 IRRs
    - Note that IRRs are not dose-dependent events. They may occur even after a small amount of drug has been administered.
    - Grade 3 diarrhea that responds to adequate therapy within 48 hours
    - Grade 3 nausea or vomiting that occurs in the absence of premedication and responds to adequate therapy within 72 hours
- *Any increase in hepatic transaminase > 3 • baseline and an increase in direct bilirubin > 2 • ULN, without any findings of cholestasis or jaundice or signs of hepatic dysfunction and in the absence of other contributory factors (e.g., worsening of metastatic disease or concomitant exposure to known hepatotoxic agent or of a documented infectious etiology) is suggestive of potential drug induced liver injury (according to Hy's Law) and will be considered a DLT*
- Hematologic adverse events that meet any of the following criteria:
  - Grade 3 or 4 neutropenia in the presence of sustained fever of >38°C (lasting >5 days) or a documented infection
  - Grade 4 neutropenia lasting >7 days
  - Grade 3 or 4 thrombocytopenia *if associated with Grade ≥ 3 bleeding*
  - Grade 4 thrombocytopenia lasting >7 days

Other toxicities that are considered clinically relevant and related to study treatment as determined by the investigator and the Medical Monitor may also be considered DLTs.

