### **3.1.2            Dose-Escalation Phase (Part 1)**

The purpose of the dose-escalation phase (Part 1) is to identify the RP2D *and regimen* for idasanutlin when combined with a fixed dose of 1000 mg of obinutuzumab in patients with R/R FL and *the RP2D for idasanutlin when combined with 375 mg/m^2 of rituximab in patients with R/R DLBCL*. The RP2D will be based on MTD of idasanutlin when combined with a fixed dose of obinutuzumab *or with 375 mg/m^2 of rituximab*, but will also include all safety data during treatment. *There could be two different RP2Ds and/or regimens dependent on the combinations of idasanutlin plus obinutuzumab or idasanutlin plus rituximab.*

During the escalation phase, approximately 9• 40 patients will be enrolled in dosing groups of 3• 6 patients each and will be treated at escalating doses of idasanutlin in accordance with the treatment regimen and dose-escalation rules described in Section 3.1.2.2.

Patients will be closely monitored for adverse events during a DLT assessment window, defined as the first treatment cycle *for Regimen A and the first two treatment cycles (one cycle of idasanutlin combination treatment) for patients enrolled in bridging cohort(s) in which idasanutlin will start at Cycle 2 (Regimen B)*. See Section 3.1.2.2 for treatment regimens. Adverse events meeting the criteria for DLT, as defined below (see Section 3.1.2.1), will be reported to the Sponsor within 24 hours (see Section 5.4.2).

Patients experiencing a DLT during the *DLT window* will permanently discontinue study treatment.

Patients who discontinue from the study prior to completing the DLT assessment window for reasons other than a DLT will be considered non-evaluable for dose-escalation decisions and MTD assessments and will be replaced by an additional patient at that same dose level who has not been previously treated in the study. Patients who miss one or more doses of obinutuzumab, *rituximab*, or idasanutlin during the DLT assessment window for reasons other than a DLT will also be replaced.

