### 5.2.1 Adverse Events

According to the ICH guideline for GCP, an adverse event is any untoward medical occurrence in a clinical investigation subject administered a pharmaceutical product, regardless of causal attribution. An adverse event can therefore be any of the following:

- Any unfavorable and unintended sign (including an abnormal laboratory finding), symptom, or disease temporally associated with the use of a medicinal product, whether or not considered related to the medicinal product
- Any new disease or exacerbation of an existing disease (a worsening in the character, frequency, or severity of a known condition), except as described in Section 5.3.5.10
- Recurrence of an intermittent medical condition (e.g., headache) not present at baseline

- Any deterioration in a laboratory value or other clinical test (e.g., ECG, X-ray) that is associated with symptoms or leads to a change in study treatment or concomitant treatment or discontinuation from study drug
- Adverse events that are related to a protocol-mandated intervention, including those that occur prior to assignment of study treatment (e.g., screening invasive procedures such as biopsies)

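### Section 3.1.2.1 counts some events that are unequivocally unrelated to study treatment as dose-limiting toxicities, which ends the patient's treatment and feeds the mCRM

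*Combined protocol and SAP*

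**What the plan says.** The lead-in to Section 3.1.2.1 applies one causal filter to every listed criterion: the event must be "assessed by the investigator as not clearly related to the patient's underlying disease". Two criteria carry a further exemption. The fatal-event criterion reads "Any Grade 5 adverse event unless unequivocally due to the underlying malignancy or extraneous causes", and the hepatic criterion applies only "in the absence of other contributory factors".

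The delay criterion has no such wording: "Adverse event of any grade that leads to a delay of more than 14 days in the start of the next treatment cycle". The Grade 3-4 non-hematologic criterion excepts infusion-related reactions, certain diarrhea and certain nausea or vomiting, and none of these exceptions concerns cause. The closing sentence of the section lets the investigator and Medical Monitor add "Other toxicities that are considered clinically relevant and related to study treatment".

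Section 5.2.1 defines an adverse event as "any untoward medical occurrence in a clinical investigation subject administered a pharmaceutical product, regardless of causal attribution". Under Section 3.1.2 a patient with a DLT in the window "will permanently discontinue study treatment", and Section 4.6.2 repeats this. Section 3.1.2.3 updates the mCRM posterior with the observed DLTs and lets clinical judgment override the recommended dose.

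**The concern.** The rule is more lenient for the worse outcome. A death in a road accident is not a DLT, but a Grade 3 fracture from the same accident is. The closing sentence of Section 3.1.2.1 does not help, because it can add DLTs but cannot remove one.

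Two things are at stake. The patient loses a treatment that did no harm; FL patients enter only when the investigator sees no more appropriate option (Section 4.1.1). The dose-toxicity model also receives an event that carries no information about dose.

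**Working it through.** **1. Causal tests within Section 3.1.2.1**

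| Criterion | Exemption beyond the lymphoma filter |
|---|---|
| Grade 5 | Yes: extraneous causes, if unequivocal |
| Hepatic | Yes: other contributory factors |
| Delay of more than 14 days | None |
| Grade 3-4 non-hematologic | None on cause |
| Hematologic | None |

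No other section limits the listed DLTs to treatment-related events. The Grade 5 and hepatic criteria were added in protocol Version 4, and both carry an exemption. The gap therefore looks like a drafting omission, although the documents do not say so.

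**2. The same event outside the DLT rule**

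Section 4.6.2 stops treatment for a Grade 3 or higher non-hematologic event only if it is reasonably possible that treatment caused it, and it is life threatening or fails to resolve in time. Table 19 holds treatment for any such event but modifies the dose only for related ones. In Regimen A, an unrelated Grade 3 fracture thus means a permanent stop in Cycle 1, but a hold and resumption in Cycle 2.

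**3. Loss to the patient**

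- Grade 3-4 event in Cycle 1 of Regimen A: up to 6 − 1 = 5 of 6 induction cycles, plus maintenance for an FL patient who would have responded.
- Delay criterion: Section 4.6.2 separately stops treatment for any adverse event delaying the next cycle by more than 21 days. The DLT rule alone is decisive for delays of 15 to 21 days.

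**4. Reproducing the plan's recommendations**

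Inputs from Section 3.1.2.3: logit p(d) = log α + β·log(d/300); independent normal priors on log α and log β with means −1.237 and 0.460 and variances 2.661 and 1.816; loss weights 1, 0, 1, 2; and a 151% increment cap up to 300 mg. The dose that minimises expected loss on a grid gives:

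- 0, 1, 2 DLTs of 3 at 100 mg: 250, 100, 50 mg, as stated in the plan.
- Then, after 0 of 3 at 100 mg, 0, 1, 2 of 3 at 250 mg: 300, 250, 200 mg, as stated.
- Then, after no DLTs at 100 and 250 mg, 0, 1 of 3 at the first 300 mg cohort: 300, 300 mg, as stated.
- 3 of 3 at 250 mg: 150 mg, against 100 mg in the plan. This does not bear on the point.

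Counting one unrelated event moves the posterior mean DLT risk at 100 mg from 0.05 (0 of 3) to 0.23 (1 of 3). At 250 mg it moves from 0.09 to 0.23.

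**5. Effect on the next dose, from the plan's own figures**

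The no-DLT path is in the text of Section 3.1.2.3, and the 1- and 2-DLT columns are in Table 5 (cohorts of 3).

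| Current dose (mg) | 0 DLT | 1 DLT | 2 DLTs | Withheld, 0 to 1 | Change, 1 to 2 |
|---|---|---|---|---|---|
| 100 | 250 | 100 | 50 | 150 | −50 |
| 250 | 300 | 250 | 200 | 50 | −50 |
| 300 (first) | 300 | 300 | 250 | 0 | −50 |
| 300 (second) | 350 | 300 | 300 | 50 | 0 |
| 350 | 400 | 350 | 300 | 50 | −50 |
| 400 | 450 | 400 | 350 | 50 | −50 |
| 450 | 500 | 450 | 400 | 50 | −50 |
| 500 | 600 | 500 | 450 | 100 | −50 |
| 600 | 700 | 650 | 550 | 50 | −100 |

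The last row of Table 5 (750 mg) has no counterpart on the no-DLT path. An unrelated event that is the cohort's only DLT usually withholds one 50 mg step. If it joins one genuine DLT, the next dose can fall below the current dose.

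**6. Frequency (assumption)**

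The documents give no rate q of unrelated qualifying events per patient. With P = 1 − (1 − q)³, assumed values of 1%, 2% and 5% give 3.0%, 5.9% and 14.3% for at least one in a cohort of 3. Over 9 to 40 patients, q = 1% implies 0.09 to 0.40 expected events, and q = 5% implies 0.45 to 2.0.

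**The case against.** The best defence is that this is a deliberately strict default. A single filter keeps investigator attribution out of the DLT count in an open-label study, and any error is toward caution. Appendix 11, Table 2 gives a reason for caution: an excessively toxic dose is recommended 35% of the time when the prior is right, and 63% or 67% when toxicity is 30% or 80% higher. The Sponsor may override the model, and dose decisions take in all safety data. The events may be rare, and a patient who misses a window dose "during the DLT assessment window for reasons other than a DLT will also be replaced" anyway, so the exemption will not always save an observation.

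Much of this stands, and it makes the escalation effect secondary. It does not reach the patient. The override concerns dose selection; it neither reclassifies the event nor restores treatment. Strictness also does not explain exempting a death but not a fracture, and an unequivocal standard keeps every doubtful event as a DLT.

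Four further inferences need care:

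- *The MTD will be materially underestimated.* The documents do not support this, because they give no event rate and the Sponsor can override.
- *The cohorts needed to recover from one such DLT can be counted.* The plan states no multi-cohort path after a DLT. The grid model above stays at 300 mg on the DLT-free path, where the plan climbs to 800 mg, so it cannot supply one.
- *Such an event can only hold the dose, never lower it.* Table 5 shows otherwise when a genuine DLT is also present.
- *Every long delay is affected.* Beyond 21 days Section 4.6.2 stops treatment anyway, although Table 19 words its own 21-day stop more narrowly, for toxicity attributable to treatment.

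**Conclusion.** The point holds as a rule that gives the wrong result in identifiable cases. The main harm is mandatory, needless loss of treatment: up to 5 of 6 induction cycles in Regimen A, and maintenance in FL. Five cycles is a ceiling, for an event in Cycle 1. The effect on escalation is smaller, conservative in direction and open to override. It is usually one withheld 50 mg step, 150 mg after the first cohort, and a lower dose only alongside a genuine DLT.

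The conclusion assumes that the criteria are applied as written and that Section 4.6.2 governs delays beyond 21 days. How often it will matter is unknown. The change is worth making because it is small and uses the plan's own standard; the present rule does not make the trial unsafe.

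**What to change.** Keep the present lead-in filter, "assessed by the investigator as not clearly related to the patient's underlying disease", and add after it: *and not unequivocally due to extraneous causes*. State that this applies to every listed criterion. Then:

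- Have the investigator and Medical Monitor document the reason for each exempted event before the next mCRM update, using the per-drug causality assessment already required by Section 5.3.4.
- Keep the event in the adverse event tables.
- Manage the patient under Table 19 (hold, then resume on recovery), leaving the 21-day stop in Section 4.6.2 unchanged.
- Replace the patient under Section 3.1.2 if a window dose was missed. In Regimen A, a patient who received all window doses and only starts Cycle 2 late has completed the window and counts as evaluable without a DLT.

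The costs are slightly more reliance on attribution in an open-label study, limited by the unequivocal standard; a protocol amendment with the approvals in Section 9.6; and a stated decision on re-adjudicating patients already treated. That decision is needed because enrollment had begun (1 patient by 1 May 2016, Section 5.1.3) and the mCRM uses DLT data cumulatively.

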### 3.1.2.2 Treatment Regimens

Induction treatments will be administered in 28-day cycles, as outlined in [Table 2](#). Inpatient dose escalation is not permitted in this study. The starting dose for idasanutlin will be 100 mg QD. The dose for idasanutlin will be increased by at least 50 mg from the preceding dose level. *During the dose-escalation phase, patients will be enrolled according to the schema in [Figure 6](#). Three patients will initially be enrolled in each cohort, and up to 3 additional patients can be enrolled in a cohort at the Sponsor's discretion. The first patient in each cohort will be observed for safety for 1 week after Cycle 1 Day 1 before additional patients are enrolled in the same cohort. A minimum of 3 patients enrolled in a cohort must complete at least the defined DLT window before enrollment commences in the next cohort.*

*Patients in the first cohort will begin with a starting oral dose of 100 mg of idasanutlin QD on Days 1•5 of each cycle in combination with a flat dose of obinutuzumab 1000 mg intravenous (IV) on Days 1, 8, and 15 of Cycle 1 and Day 1 of Cycles 2•6 (see [Table 2](#) and [Figure 11](#) for details on treatment regimens). This regimen is referred to as Regimen A.*

*Following the identification of the MTD for idasanutlin in combination with obinutuzumab, a bridging cohort of DLBCL patients will be opened to test this MTD in combination with rituximab (375 mg/m^2 on Day 1 of each cycle; see [Figure 6](#), [Figure 12](#), and [Table 2](#)).*

*If safety and tolerability allow, idasanutlin dose escalation may be explored in combination with rituximab in patients with DLBCL until identification of a new MTD (see [Figure 6](#)). A different RP2D in combination with rituximab maybe chosen based on a different MTD.*

*Following the identification of the MTD for idasanutlin in combination with obinutuzumab, a bridging cohort of FL patients will be opened to test this MTD in a different regimen, referred to as Regimen B. Obinutuzumab will be given alone in Cycle 1 and in combination with idasanutlin in Cycles 2•6 (see [Figure 6](#), [Figure 12](#), and [Table 2](#)).*

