**Table 2 Induction Treatment for Dose-Escalation Phase**

Dose-Escalation, FL and DLBCL Patients (28-Day Cycles): Regimen A	
Cycle 1	DLT period 
 
• Obinutuzumab 1000 mg IV on Days 1, 8, and 15
 
• Idasanutlin, oral Days 1•5, starting dose 100 mg QD, minimal clinically and pharmacologically feasible dose-escalation steps 50 mg
 

Cycles 2•6	
 
• Obinutuzumab 1000 mg IV on Day 1
 
• Idasanutlin, oral Days 1•5, starting dose 100 mg QD
 

Dose-Escalation Bridging Cohort, DLBCL Patients Only (28-Day Cycles)	
Cycle 1	DLT period 
 
• Rituximab 375 mg/m^2 IV on Day 1
 
• Idasanutlin, oral Days 1•5, starting dose MTD identified in combination with obinutuzumab with Regimen A, minimal clinically and pharmacologically feasible dose-escalation steps 50 mg
 

Cycles 2–6	
 
• Rituximab 375 mg/m^2 IV on Day 1
 
• Idasanutlin, oral Days 1•5, starting dose MTD identified in combination with obinutuzumab
 

Dose-Escalation Bridging Cohort, FL Patients Only (28-Day Cycles): Regimen B	
Cycle 1	
 
• Obinutuzumab 1000 mg IV on Days 1, 8, and 15
 

Cycles 2–6	
 
• Obinutuzumab 1000 mg IV on Day 1
 
• Idasanutlin, oral Days 1•5, starting dose MTD identified in combination with obinutuzumab with Regimen A during dose escalation, minimal clinically and pharmacologically feasible dose-escalation steps 50 mg
 

DLT period will be Cycles 1 and 2.	

*DLBCL =diffuse large B-cell lymphoma; DLT = dose-limiting toxicity; FL =follicular lymphoma; IV=intravenous; MTD =maximum tolerated dose; QD=once a day.*

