### **3.1.2.3 Dose-Toxicity Model with mCRM**

The dose escalation will employ a modified-Continual Reassessment Method with Overdose Control (mCRM) design in order to define MTD and/or the recommended dose. The design is based on the primary safety variable (the occurrence of a DLT). The MTD is defined as the dose that maximizes the probability of a DLT being in the targeted toxicity interval of 25%• 35%, subject to the probability of DLT being in the excessive toxicity interval of 35%• 100% being less than 35%. Patients within a cohort will be enrolled in a sequential manner in cohorts of at least 3 patients each, which, if required, can be expanded with additional patients. Each patient will be observed over 1 cycle (1 cycle lasts 28 days) of treatment for DLT assessment. The first patient in each cohort will be observed for safety for 1 week *after Cycle 1, Day 1* before enrolling additional patients in the cohort. After the last patient in each cohort has completed the 1-cycle DLT observation period, the Sponsor and investigators will evaluate the next dose recommended by the mCRM design and agree on the dose for the subsequent cohort. At each dose-escalation step, the dose can be escalated, de-escalated, or an additional cohort at the same dose-level can be enrolled.

The starting dose for idasanutlin will be 100 mg and the fixed dose for obinutuzumab will be 1000 mg. *The dose for rituximab starting from the bridging cohort for DLBCL patients will be 375 mg/m^2.* The dose-escalation is for the dose of idasanutlin. The maximum allowable increments for idasanutlin between dose levels will be as follows:

- 151% increase if the last idasanutlin dose is below or equal to 300 mg
- 33% of relative increase if the last idasanutlin dose is above 300 mg

The dose of idasanutlin will not be escalated above 800 mg. The selection of the next dose will be subject to clinical judgment and mandated safety constraints that limit the size of dose increments. Clinical judgment will always override mCRM recommendations in the dose-selection process.

The model-based dose escalation at each step will identify the next recommended dose level subject to the following criteria:

- The posterior probability of being within the excessive toxicity interval (above 35% DLT probability) is below 35%, and
- The posterior probability of being within the target toxicity interval (of 25%• 35% DLT probability) is maximized.

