Grade 3 or 4 hematologic toxicity a, b	
For patients who have had one, two, or no prior dose reductions:
 
 
• Withhold study treatment.a
 
• Administer RBCs or platelets as required.
 
• If patient has not already initiated G-CSF, initiate prophylactic G-CSF for current and subsequent cycles.
 
• If improvement to Grade • 2 or baseline • 14 days after the scheduled date for the next cycle, resume obinutuzumab or rituximab at full dose and resume idasanutlin at current dose.
 
• If improvement to Grade • 2 or baseline 15• 21 days after the scheduled date for the next cycle, resume obinutuzumab or rituximab at full dose and resume idasanutlin at a reduced dose according to guidelines in Section 5.1.5 for current and subsequent cycles.
 
• If study treatment is withheld for >21 days, permanently discontinue study treatment.
 
• Permanently discontinue study treatment if any of the following events occur: 
 
Grade 3 or 4 thrombocytopenia of any duration if associated with Grade ≥ 3 bleeding
 
Recurrent Grade 3 or 4 neutropenia associated with fever of > 38°C (> 5 days) or a documented infection despite use of G-CSF and after one idasanutlin dose reduction
 
Recurrent Grade 4 neutropenia or thrombocytopenia lasting more than 7 days despite use of G-CSF (for neutropenia) and after one idasanutlin dose reduction
 
 
 
 
For patients who have had three prior dose reductions or for patients who reach the lowest dose level and no further dose reduction is applicable (see Section 5.1.5):
 
 
• Permanently discontinue study treatment.
 

G-CSF = granulocyte colony-stimulating factor; NHL = non-Hodgkin's lymphoma.

a Treatment delays apply to all toxicities; dose modifications apply only to toxicities that are considered to be related to idasanutlin

b If cytopenia is thought to be caused mainly by NHL infiltration of the bone marrow, the investigator may decide not to modify dose.

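### The cycle-delay DLT criterion can mature up to about 15 days after the window that gates escalation, and the plan does not say whether the dose decision waits or how a pending case is coded

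*Combined protocol and SAP*

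**What the plan says.** Section 3.1.2.1 lists among the DLTs an "Adverse event of any grade that leads to a delay of more than 14 days in the start of the next treatment cycle", provided the event arises in the first cycle (first two cycles in the FL bridging cohorts). Grade 4 neutropenia or thrombocytopenia lasting more than 7 days is also a DLT.

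The window is "defined as the first treatment cycle" for Regimen A (Section 3.1.2). Section 3.1.2.3 fixes its length: "Each patient will be observed over 1 cycle (1 cycle lasts 28 days) of treatment for DLT assessment". For Regimen B, Table 2 states: "DLT period will be Cycles 1 and 2".

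On when to decide, Section 3.1.2.3 says: "After the last patient in each cohort has completed the 1-cycle DLT observation period, the Sponsor and investigators will evaluate the next dose". Section 3.1.2.2 sets the same point for the dose evaluation and adds a condition for opening the next cohort: "A minimum of 3 patients enrolled in a cohort must complete at least the defined DLT window before enrollment commences in the next cohort".

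The non-evaluability and replacement rules in Section 3.1.2 cover patients who leave the study before finishing the window, or who miss doses within it, for reasons other than a DLT. They do not mention a patient who has finished the window but whose next cycle is on hold.

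On what follows a DLT, Section 3.1.2 says that patients with a DLT in the window "will permanently discontinue study treatment", and Section 4.6.2 agrees. Table 17 (Section 5.1.5.1) handles Grade 3 or 4 hematologic toxicity by time to recovery. Two of its rows contain the words "days after the scheduled date for the next cycle, resume obinutuzumab"; the second, for recovery on days 15 to 21, restarts idasanutlin at a reduced dose. No exception for the DLT window is stated.

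**The concern.** In Regimen A a delay in starting Cycle 2 begins, by definition, after the 28-day window has closed. The criterion can therefore never be confirmed inside the window, yet completion of the window is what permits the next dose decision. A patient whose Cycle 2 is on hold at that point has an open DLT status, and the plan provides no category for it.

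The other criteria do not fully close the gap. Table 17 holds treatment for Grade 3 or 4 hematologic toxicity until recovery to Grade 2 or baseline. Persistent Grade 3 thrombocytopenia without Grade 3 or higher bleeding, or Grade 3 neutropenia without sustained fever or documented infection, meets none of the hematologic DLT criteria. Apart from the discretionary clause on other toxicities, only the delay criterion would capture it.

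Cytopenia matters here. Section 1.4 names thrombocytopenia and neutropenia as the main DLTs seen earlier with idasanutlin, and Table 14 gives Grade 3 or higher rates of 44% and 27% on idasanutlin alone. What is at stake is whether the overdose control works on complete data: if a pending DLT is left out, the next cohort may be dosed higher than the model would recommend with it included.

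**Working it through.** **Timing.** Inputs: 28-day cycles, delay limit 14 days, duration limit 7 days.

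- Regimen A: window ends Day 28; Cycle 2 Day 1 is due on Day 29; 29 + 14 = Day 43. The criterion is met once Day 43 passes without a start. Gap: 43 − 28 = 15 days.
- Regimen B: window ends Day 56; Cycle 3 Day 1 is due on Day 57; 57 + 14 = Day 71. Gap: 71 − 56 = 15 days.
- Grade 4 cytopenia, Regimen A: onset on Day 22 gives exactly 7 days by Day 28, so onset on Day 22 or later cannot exceed 7 days inside the window. In Appendices 1 and 2 the scheduled Cycle 1 blood counts are on Days 1, 8 and 15, and the next falls within 72 hours before Cycle 2 Day 1. A Grade 4 value first seen at that last count cannot have a documented duration above 7 days by Day 28.

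The 15 days are a maximum. The first patient in a cohort is observed for 1 week before others enrol, so when a later patient reaches Day 28 the first is at about Day 35 or beyond, leaving 43 − 35 = 8 days or less.

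**Effect of one DLT on the next dose.** From the text of Section 3.1.2.3 and Table 5, cohorts of 3, no earlier DLTs:

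| Current cohort | Next dose, 0/3 DLTs | Next dose, 1/3 DLTs |
|---|---|---|
| 100 mg | 250 mg | 100 mg |
| 250 mg | 300 mg | 250 mg |
| 300 mg (first) | 300 mg | 300 mg |

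**Reproducing these figures.** The model is logit p(d) = log α + β·log(d/300), with log α ~ N(−1.237, 2.661) and log β ~ N(0.460, 1.816), the second entries read as variances and no correlation. The recommended dose minimises expected loss with weights [1, 0, 1, 2], subject to the 151% maximum increase. A grid posterior gives 11 of the 12 stated recommendations for 0 to 3 DLTs in cohorts at 100, 250 and 300 mg, including all six cells in the table. The exception is 3 DLTs at 250 mg (150 mg computed, 100 mg stated). The six cells are unchanged if the 35% overdose limit is added.

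**Posterior probability that the DLT rate exceeds 35%, at the dose chosen when the DLT is left out:**

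- Cohort at 100 mg, next dose 250 mg: 0.13 with 0/3 entered, 0.51 with 1/3 entered.
- Cohort at 250 mg (after 0/3 at 100 mg), next dose 300 mg: 0.13 with 0/3 entered, 0.39 with 1/3 entered.

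Section 3.1.2.3 requires this probability to be below 0.35. With the DLT included, both doses fail that limit.

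**Consequence of a 15 to 21 day delay after Cycle 1.** Sections 3.1.2, 3.1.2.1 and 4.6.2 together make it a DLT with permanent discontinuation. Table 17 resumes treatment with idasanutlin reduced. Both apply on their face to the same escalation patient.

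**The case against.** A reader might infer that the plan scores a pending patient as having no DLT. The documents do not say so; they are silent. Completing the window is also the earliest permitted time for the decision, not a fixed date: Section 3.1.2.2 speaks of at least the window, and both sections place the evaluation after the last patient has finished.

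Several safeguards exist. The dose review includes adverse event, laboratory and dose-administration data, so a held cycle would be visible. Clinical judgement takes precedence over the model. The investigator and Medical Monitor may class other relevant toxicities as DLTs. Grade 3 or higher neutropenia and thrombocytopenia are reportable within 24 hours (Section 5.2.3). DLT data are cumulative, so a late DLT enters the following update. The next cohort starts with one patient observed for a week. Many severe cytopenias will already be DLTs on other criteria by Day 28.

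All of this stands and lowers the risk. It does not remove it: discretion to wait is not a rule on coding, and a late DLT may enter the model after the next cohort has been dosed.

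A reader might also infer from Table 14 that long delays will be common. The table pools 34 patients over 100 to 800 mg/day and gives neither duration nor onset. Section 5.1.3.2 treats prolonged thrombocytopenia as a possibility and calls the clinical data on duration limited. At the 100 mg start, Section 3.3.2 reports no Grade 3 or 4 hematologic toxicity at the roughly equivalent single-agent dose of the older formulation.

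On Table 17, one can argue that the DLT-specific sections govern over general guidance. That may be the intention, but it is not written.

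**Conclusion.** The mismatch is real and goes beyond missing detail. The delay criterion can mature up to about 15 days after the window that gates escalation, and late-onset Grade 4 cytopenia has the same problem on a 7-day scale. Because the plan neither makes the decision wait nor says how an unresolved case is coded, a pending DLT can be left out of the update.

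One uncounted DLT changes the plan's own recommendation from 100 to 250 mg or from 250 to 300 mg, in both cases to a dose that fails the plan's overdose limit once the DLT is counted. It has no effect at the first 300 mg cohort.

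These sizes assume cohorts of 3, no earlier DLTs, and one patient whose event later meets the criterion and is omitted at the decision. The frequency of such delays is not given, so the expected number of affected cohorts cannot be computed. Given the existing review, override and cumulative updating, this is a should-fix. The Table 17 conflict is a separate inconsistency to be resolved in the same amendment.

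**What to change.** Reconcile the timing of the dose evaluation and the definition of a DLT-evaluable patient in Sections 3.1.2.2 and 3.1.2.3 with the DLT definition in Section 3.1.2.1, so that a patient's DLT status enters the mCRM update only once the plan's existing criteria can be read for that patient. Cover both regimens. This adds no new toxicity threshold. It needs a few sentences in an amendment and, in affected cohorts only, a wait of up to about 15 days.

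Separately, reconcile the 15 to 21 day row of Table 17 with Sections 3.1.2, 3.1.2.1 and 4.6.2 for escalation patients in the DLT window. Which rule applies is for the sponsor and its clinical advisers to decide; the documents should give one answer.
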